6.1.1. Screening Visit

The following procedures must be completed no more than 1 month prior to enrollment and no more than 4 weeks following enrollment.

- Informed Consent
- Demographics
- Medical History
- Previous therapy
- Surgical report will include date and type of surgery +/- lymphadenectomy
- Radiotherapy report will include modality of therapy with prescribed dose and field and dates of therapy
- Previous systemic (hormonal, chemo, other) therapy – drugs, doses, dates of therapy
- Complete Physical Exam including height and weight
- Brief Pain Inventory
- Vital Signs
- ECOG Performance Status
- CBC with differential and platelet count
- CMP (with direct bilirubin with known Gilbert's syndrome)
- PSA
- Testosterone
- CTC count via CellSearch methodology (may be collected prior to treatment C1D1, do not need to repeat if has known result within 1 month of C1D1)
- CTC for Research (may be collected prior to treatment C1D1)
- Cell-Free DNA BCT[®] Research blood sample (may be collected prior to treatment C1D1)
- Immune research blood sample (may be collected prior to treatment C1D1)
- CT or MRI (abdomen-pelvis), up to 1 month prior to enrollment
- Bone scan, up to 1 month prior to enrollment
- Any confirmatory tests to assess equivocal results of bone scan should also be completed within a month of enrollment
- CXR, up to 1 month prior to enrollment (CXR waived if CT chest performed)
- Single intravenous dose of ⁶⁸Ga-PSMA-HBED-CC (5±2mCi or 185±74MBq) at least 1 week prior to ¹⁷⁷Lu-PSMA-617 infusion
- ⁶⁸Ga-PSMA-HBED-CC PET/CT scan to confirm the PSMA expression at the tumor site(s). PET/CT scans will be obtained 1 to 3 hours after the infusion of ⁶⁸Ga-PSMA-HBED-CC
- Archival tissue for PSMA expression and genomic studies to identify DNA damage

Screening (except ^{68}Ga -PSMA-HBED-CC PET/CT scan) and visit #1 may occur on the same day provided results are available, all entry criteria are met, and the subject is registered on the study prior to dosing. In this instance, duplicate procedures do not need to be performed.

6.1.1.1. Re-screening

Subjects who are unable to complete the initial screening or are not initially eligible will be permitted undergo repeat screening (with repeat written informed consent).

6.1.2. Treatment Phase

The treatment and early monitoring phase comprises of 8 visits spanning over approximately 12 weeks.

Absolute neutrophil counts, platelet counts, bilirubin, transaminases, and serum creatinine must be performed with results available and within range of eligibility criteria within 1 week prior to treatment initiation on C1D1.

Details for each visit are listed below:

6.1.2.1 ^{177}Lu -J591 and ^{177}Lu -PSMA-617 infusion (Treatment 1 Day 1) and (Treatment 2 Day 15 \pm 1 day)

The following procedures must be completed on the day of treatment:

- Targeted Physical Examination with vital signs and weight
- Medical History
- Brief Pain Inventory, FACT-P
- ECOG Performance Status
- CBC with differential and platelet count
- CMP (with direct bilirubin with known Gilbert's syndrome)
- PSA
- LDH
- Intravenous dose of ^{177}Lu -PSMA-617 (Dose based on the Cohort in which the subject is enrolled) and ^{177}Lu -J591
- Adverse event evaluation
- Concomitant medications
- Concomitant procedures
- Planar/SPECT imaging (on D15 prior to treatment in consenting subjects)

As stated above, Absolute neutrophil counts, platelet counts, bilirubin, transaminases, and renal function assessment must be available within 1 week prior to treatment on D1 and meet eligibility criteria.

For treatment #2 (D15), grade ≥ 2 thrombocytopenia or neutropenia within 24 hours of the second dose of ^{177}Lu -PSMA products (Visit 3) requires a subject's treatment to be held until the toxicity has resolved to least grade 1. If the toxicity has not resolved after 2 weeks of monitoring, the subject's ^{177}Lu -PSMA product treatment will be permanently discontinued and will be termed dose-limiting toxicity

6.1.2.2 Imaging visit (Day 8 \pm 1) [optional D1, D4, D15 in consenting subjects]

- Planar/SPECT imaging
- Targeted Physical Examination with vital signs and weight
- Medical History
- Brief Pain Inventory, FACT-P
- ECOG Performance Status
- CBC with differential and platelet count
- CMP (with direct bilirubin with known Gilbert's syndrome)
- Adverse event evaluation
- Concomitant medications

6.1.2.2 Follow-up visits: Follow up Visit 1 (Day 22 \pm 3), Follow up Visit 2 (Day 29 \pm 3), Follow up Visit 4 (Day 57 \pm 3)

- Targeted Physical Examination with vital signs and weight
- Medical History
- Brief Pain Inventory, FACT-P
- ECOG Performance Status
- CBC with differential and platelet count
- CMP (with direct bilirubin with known Gilbert's syndrome)
- PSA (Follow up visits 2 & 4)
- LDH (Follow up visits 2 & 4)
- Adverse event evaluation
- Concomitant medications

6.1.2.3 Follow-up lab visits: Follow up Visit 3 (Day 43 \pm 3); Follow up Visit 5 (Day 71 \pm 3)

- CBC with differential and platelet count
- CMP (with direct bilirubin with known Gilbert's syndrome)
- PSA
- LDH

Lab visits may be performed at any CLIA certified lab

6.1.3. Efficacy Evaluation (scan) Visit (Day 85 ± 7; note that these study procedures are not expected to occur on a single day)

The following procedures must be completed during the efficacy visit(s):

- Targeted Physical Examination with vital signs and weight
- Medical History
- Brief Pain Inventory, FACT-P
- ECOG Performance Status
- CBC with differential and platelet count
- CMP (with direct bilirubin with known Gilbert's syndrome)
- PSA
- LDH
- Testosterone
- CTC count via CellSearch methodology
- CTC for research
- Cell-Free DNA BCT[®] Research blood sample
- Immune research blood sample
- Same standard radiographic imaging modality as baseline (CT/MRI and bone scan +/- CXR)
- Single intravenous dose of ⁶⁸Ga-PSMA-HBED-CC (5±2mCi or 185±74MBq)
- PET/CT scan will be obtained between 1 and 3 hours post-injection of ⁶⁸Ga-PSMA-HBED-CC
- Adverse event evaluation
- Concomitant medications
- Concomitant procedures

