|---------------------------------------|-------------|-------|-------------------|-----------------|-----------------|
| | 65 | 70 | 70 (35 + 35) | 80 (40 + 40) | 90 (45 + 45) |
| Cumulative Dose (mCi/m ²) | 65 | 70 | 70 (35 + 35) | 80 (40 + 40) | 90 (45 + 45) |
| Platelets Grade 4 | 27% | 56.3% | 40% | 50% | 58.8% |
| Platelet Transfusion | 7% | 41% | 0% | 31.3% | 52.9% |
| Neutropenia Grade 4 | 0% | 37.5% | 0% | 31.3% | 29.4% |
| Febrile Neutropenia | 0% | 2.1% | 0% | 0% | 5.8% |

In addition, fractionated dosing allowed concurrent dosing with myelosuppressive chemotherapy:

ii) Phase I trial of fractionated dose ¹⁷⁷Lu–J591 plus docetaxel/prednisone in men with metastatic castration–resistant prostate cancer (42):

Following progression on primary hormonal therapy, chemotherapy can offer symptomatic improvement as well as incremental survival benefit. However, responses are transient and all men eventually suffer from progression of disease as described above with single–agent anti–PSMA based radioimmunotherapy. The combination of taxane chemotherapy with radiotherapy has been used in several diseases because of the radiosensitizing effects of taxane–based chemotherapy. In addition to favorable results from fractionated RIT and the radiosensitizing effects of taxane–based chemotherapy, it is hypothesized that the additional debulking by chemotherapy will overcome some of the limits imposed by the physical characteristics of ¹⁷⁷Lu. Based upon this theory, a phase I trial of docetaxel and prednisone with escalating doses of fractionated ¹⁷⁷Lu–J591 was initiated. 15 men with median age 69.1 (49.3–80.8) were enrolled. The MTD/RP2D of ¹⁷⁷Lu–J591 was 40 mCi/m²x2 doses (delivered with cycle 3 of docetaxel), with 73.3% showing >50% PSA decline, 80.0% reporting >30% PSA decline, and 86.7% with any PSA decline. Predictable, reversible myelosuppression was seen. Even at the highest dose level, no dose limiting toxicity was observed, with short–term / reversible grade 4 neutropenia in 33% and grade 4 thrombocytopenia in 13%.

Aside from the overall rates of dose limiting toxicity, the combined studies have also consistently demonstrated the kinetics of myelosuppression, with nadir neutrophil and platelet counts 28–32 days following the last administered dose of ¹⁷⁷Lu–J591.

With small–molecule radioligand therapy, both the predicted and reported toxicities are much different. One would predict very little myelosuppression, but if it were to occur, it would be

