4. OVERVIEW OF STUDY DESIGN AND METHODOLOGY

4.1 Study Design

This is an open-label, single-center Phase I dose-escalation study designed to determine the dose-limiting toxicity (DLT) and the maximum tolerated dose (MTD) of combination of ¹⁷⁷Lu-J591 and ¹⁷⁷Lu-PSMA-617 in a two-week dose-fractionation regimen. ¹⁷⁷Lu-J591 will be given at a moderate dose previously demonstrated to be safe x2 infusions two weeks apart. For ¹⁷⁷Lu-PSMA-617 the dose escalation will start at 3.7 GBq (100 mCi) and escalate in increments of 1.85 GBq (50 mCi) for each dose to a planned maximum of 9.25 GBq (250 mCi) x2 doses, 2 weeks apart. Should there be unacceptable toxicity at the initial dose level, we will de-escalate to dose level -1 (1.85 GBq / 50 mCi per dose). After the phase I study has established a MTD, the Phase II, single-arm trial will start.

Patients must have documented progressive metastatic CRPC disease based on Prostate Cancer Working Group 3 (PCWG3) criteria in order to be eligible for enrollment. Upon meeting the inclusion and exclusion criteria and signing the informed consent and HIPPA form, subjects will undergo the screening. As part of the screening, subjects will get a single dose of ⁶⁸Ga-PSMA-HBED-CC and will have a PET/CT. Nuclear Medicine physician(s) will review the PET/CT scans to document PSMA expression at tumor site(s).

Subjects will have Lutetium-177 Planar/SPECT Imaging on Day 8 (±1 day) after the first dose of ¹⁷⁷Lu-J591 + ¹⁷⁷Lu-PSMA-617. Optimal images will be performed on selected consenting subjects between the initial treatment visit #1 on Day 1 and Day 4 and prior to treatment visit #2 on D15 ±1. Subjects will be closely monitored for AEs (weekly x2 weeks, then every 2 weeks for one month, at 8 and 12 weeks, and then every 4 weeks for next 3 months).

Upon completion of investigational treatment with dose-fractionation regimen of the combination of ¹⁷⁷Lu-J591 + ¹⁷⁷Lu-PSMA-617, subjects will undergo ⁶⁸Ga-PSMA-HBED-CC injection and same day PET/CT at the end of study visit to document treatment response. Subsequently survival data and additional treatment(s) information will be captured from their routine Standard of care (SOC) visits.

Table 14: Phase I dose-escalation plan for combination of ¹⁷⁷Lu-J591 + ¹⁷⁷Lu-PSMA-617:

| ¹⁷⁷Lu–J591 + ¹⁷⁷Lu–PSMA–617: Dose escalation (per dose) | | |
|--|----------------------------------|----------------------------------|
| | ¹⁷⁷Lu–J591* | ¹⁷⁷Lu–PSMA–617 |

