6.1 Schedule of Evaluations

Table 15: Schedule of trial events:

| | Screening | Treatment Visit 1 | Imaging visit | Treatment Visit 2 | F/U Visit 1 | F/U Visit 2 | F/U Visit 3 | F/U Visit 4 | F/U Visit 5 | Scan / Efficacy Visit | Short-Term F/U ^k | Long-Term F/U |
|--|-----------|-------------------|---------------|-------------------|-------------|-------------|-------------|-------------|-------------|-----------------------|-----------------------------|----------------|
| Informed Consent | x | | | | | | | | | | | |
| Demographics | x | | | | | | | | | | | |
| Medical History | x | x | x | x | x | x | | x | | x | x | |
| Physical Exam | x | x | x | x | x | x | | x | | x | x | |
| Performance Status | x | x | x | x | x | x | | x | | x | x | |
| Vital Signs ^a | x | x | x | x | x | x | | x | | x | x | |
| PRO ^l | x | x | x | x | x | x | | x | | x | x ^l | |
| CBC with diff, plts ^b | x | x | x | x ^c | x | x | x | x | x | x | x | |
| Serum Chemistry ^d | x | x | x | x | x | x | x | x | x | x | x | |
| PSA | x | x | | x | | x | | x | | x | x | |
| LDH | | x | | x | | x | | x | | x | x | |
| Testosterone | x | | | | | | | | | x | | |
| CTC Count ^e | x | x ^e | | | | | | | | x | | |
| CTC for Research ^f | x | x ^f | | | | | | | | x | | |
| Cell-Free DNA Research sample ^g | x | x ^g | | | | | | | | x | | |
| Immune research sample ^m | x | x ^m | | | | | | | | x | | |
| ⁶⁸ Ga-PSMA infusion & PET CT | x | | | | | | | | | x | | |
| Radiographic evaluation ^h | x | | | | | | | | | x | x ^h | x ^h |
| ¹⁷⁷ Lu-J591 infusion | | x | | x | | | | | | | | |
| ¹⁷⁷ Lu-PSMA-617 infusion | | x | | x | | | | | | | | |

| | | | | | | | | | | | | |
|---|---|---|----------------|----------------|---|---|--|---|--|---|---|---|
| ¹⁷⁷ Lu-Planar/SPECT imaging ⁱ | | | x ⁱ | x ⁱ | | | | | | | | |
| Archival Tissue | x | | | | | | | | | | | |
| Adverse Event Monitoring | | x | x | x | x | x | | x | | x | x | |
| Concurrent Medications | x | x | x | x | x | x | | x | | x | x | |
| Survival Assessment ^j | | | | | | | | | | | | x |

- a: Vital signs will include height and weight during screening and at least weight thereafter
- b: Any subject with grade >2 neutropenia or thrombocytopenia at any time point will be followed at least weekly until resolution to grade 1

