6.1.4 Short term follow up (q4 week visits x3 following Efficacy/Scan visit)

Unless subjects have radiographic progression, withdraw from study, or initiate new treatment, the following procedures must be completed every 4 weeks (+/- 7 days) after the initial efficacy/scan visit:

- Targeted Physical Examination with vital signs and weight
- Interim Medical History
- ECOG Performance Status
- CBC with differential and platelet count
- CMP (with direct bilirubin with known Gilbert's syndrome)
- PSA
- LDH

These q4-week lab/clinic visits may be performed with any licensed provider at any CLIA certified lab, provided that the results are available/provided to the Investigator within allowable windows. Visits associated with repeat CT and bone scan (q12 weeks until radiographic progression) should be performed at the WCM investigative site.

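### Section 4.1 puts an adverse-event check at week 6 (Day 43), but Table 15 and Section 6.1.2.3 make that visit labs only, so no AE evaluation is scheduled between Day 29 and Day 57

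*Combined protocol and SAP*

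**What the plan says.** - Section 4.1 (Study Design) sets the AE monitoring frequency as "weekly x2 weeks, then every 2 weeks for one month, at 8 and 12 weeks, and then every 4 weeks for next 3 months".
- Section 6.1, Table 15, has the AE row "Adverse Event Monitoring | | x | x | x | x | x | | x | | x | x". Read against the column heads, it is marked at both treatment visits, the imaging visit, F/U Visits 1, 2 and 4, the scan/efficacy visit and short-term follow-up. It is blank at F/U Visits 3 and 5. The concurrent-medications row is blank at the same two visits.
- Section 6.1.2.3, "Follow-up lab visits: Follow up Visit 3 (Day 43" (window ±3 days), lists CBC, CMP, PSA and LDH and nothing else. It allows the draw at an outside CLIA-certified laboratory.
- Section 2.7, part B, reports "nadir neutrophil and platelet counts 28–32 days following the last administered dose" of 177Lu-J591.
- Table 15, footnote b, provides a safety net for counts: "Any subject with grade >2 neutropenia or thrombocytopenia at any time point will be followed at least weekly until resolution to grade 1".
- Section 12.5.1 counts DLT from Treatment Visit 1 to the efficacy visit. Section 6.2.10 includes in DLT both grade 4 hematologic toxicity and grade >2 non-hematologic toxicity that is at least possibly related.
- Section 6.1.4 says "the following procedures must be completed every 4 weeks (+/- 7 days) after the initial efficacy/scan visit". The list that follows has examination, interim history, performance status and laboratory tests, with no AE evaluation and no concomitant medications. Table 15 marks both for these visits.

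**The concern.** The design section and the operational schedule disagree about one AE assessment, and the disputed visit falls where the protocol's own background predicts the lowest counts. Sites work from the visit tables and lists, so the labs-only version is the one likely to be followed. A blood draw shows the counts. It does not show fever, infection, bleeding, dry mouth or other symptomatic toxicity, and it does not prompt anyone to ask about transfusions or new medication.

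DLT is the Phase I primary endpoint. Sections 4.2, 12.1 and 12.5.1 define the maximum tolerated dose as allowing no more than one DLT in six patients (Section 6.2.10 states a different limit, which is a separate matter). In cohorts this small, one event that is recorded late, graded from memory or not recorded can matter to a cohort decision.

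**Working it through.** No figure in the plan needs reproducing. The check is day arithmetic from the stated schedules.

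1. **AE days implied by Section 4.1.** Weekly for 2 weeks gives weeks 1 and 2. Every 2 weeks for one month (taken as 4 weeks) adds weeks 4 and 6. Weeks 8 and 12 follow.
   - Counted from Day 1 (Day = 1 + 7 × week): 8, 15, 29, **43**, 57, 85.
   - Counted from dose 2 (Day = 15 + 7 × week): 22, 29, **43**, 57, 71, 99.
   - Day 43 is in both lists. The Day 1 count fits better, because Section 6 schedules all on-study visits from Day 1 and the efficacy visit is on Day 85, not Day 99.

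2. **AE days actually scheduled** (Table 15 with the visit days in Sections 6.1.2 and 6.1.3): 1, 8, 15, 22, 29, 57, 85. Against the Day 1 list, Day 43 is the only one missing.

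3. **Length of the gap.**
   - Nominal: 57 − 29 = 28 days.
   - Shortest within ±3-day windows: (57 − 3) − (29 + 3) = 54 − 32 = 22 days.
   - Longest: (57 + 3) − (29 − 3) = 60 − 26 = 34 days.
   - With an AE evaluation at Day 43, the nominal gap becomes two of 14 days.

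4. **Where the nadir falls.** With dose 2 on Day 15: 15 + 28 = Day 43 to 15 + 32 = Day 47. With the ±1-day dosing window: Day 42 to 48. All of these lie inside Day 29 to 57. If dose 2 is held the full 2 weeks, to Day 29, the range becomes 29 + 28 = Day 57 to 29 + 32 = Day 61, and the Day 57 visit meets its start.

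5. **Position in the DLT window.** Section 12.5.1 runs from Day 1 to the Day 85 visit, so the whole gap is inside it. Section 12.6.1, however, makes subjects evaluable for toxicity only up to 30 days after last treatment, which is 15 + 30 = Day 45. On that rule the last scheduled AE evaluation is Day 29, and Day 57 comes too late to fill the gap.

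6. **Short-term follow-up after Day 85, side by side.**

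| Item | Section 4.1 | Table 15 | Section 6.1.4 list |
|---|---|---|---|
| AE monitoring | every 4 weeks for 3 months | marked | absent |
| Concomitant medications | not addressed | marked | absent |

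**The case against.** The strongest reply is that the protocol does not leave these four weeks unobserved. CBC and CMP are drawn at Day 43, the first day of the predicted nadir. Section 13.1 counts an abnormal laboratory finding as an AE. Section 13.1.3 has all AEs logged, and SAE reporting is not tied to visits. Cytopenia above grade 2 triggers at least weekly follow-up. The Day 57 visit takes a history, an AE evaluation and medications, and it is still inside the DLT window of Section 12.5.1. All of this stands. A reader might infer that no AE data are collected from Day 29 to Day 57, and the documents do not support that. What is missing is a scheduled clinical AE evaluation.

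A reader might also infer that dose escalation is biased upward. The documents do not show this either. Hematologic DLTs remain detectable by CBC, safety is reviewed before each escalation (Section 12.6, Interim Analysis), and the DSMB is notified after each cohort (Section 14). The plausible harm is delay, recall error and occasional loss of symptomatic events, and its size cannot be estimated from the documents.

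Two further extensions fail:
- **Day 71 (F/U Visit 5).** Counted from Day 1, Section 4.1 asks for nothing between weeks 8 and 12, so the blank cell agrees with it.
- **The timing of the blood draw.** The windows permit up to 60 − 40 = 20 days between the F/U 3 and F/U 4 counts, but the nominal interval is 14 days and no passage is contradicted. Confining F/U 3 to Day 43 to 47 would lengthen the worst-case interval from F/U 2 from 46 − 26 = 20 to 47 − 26 = 21 days.

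Finally, the month in Section 4.1 could be read as ending one month after Day 1, in which case week 6 is not required. The wording points more naturally to a month of fortnightly checks following the two weekly ones. Even on the other reading, the 28-day interval over the nadir remains.

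**Conclusion.** The point holds as an internal contradiction with a practical consequence. Section 4.1 places an AE check at Day 43, while Table 15 and Section 6.1.2.3 do not. As scheduled, there is no AE evaluation for 28 days (22 to 34 within windows), an interval that covers the predicted nadir and sits within the DLT window. The risk is late or missed symptomatic and non-hematologic DLTs, with laboratory monitoring intact.

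The second mismatch, between Section 6.1.4 and both Table 15 and Section 4.1, is real but lesser. It falls after the DLT window, and the visits still include history and examination. The written list matters there because these visits may be held with outside providers.

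The conclusion assumes that one month means 4 weeks and that dose 2 is given on Day 15 ± 1. It also assumes that the 28–32-day nadir, observed with 177Lu-J591, carries over to the combination. No sample-size, power or error-rate figure changes.

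**What to change.** 1. Reconcile Table 15 and Section 6.1.2.3 with Section 4.1 on AE and concomitant-medication collection at F/U Visit 3 (Day 43). State the time origin of the Section 4.1 schedule so that it can be read only one way.
2. Reconcile the required list in Section 6.1.4 with Table 15 and Section 4.1 on AE evaluation, and with Table 15 on concomitant medications.

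No change to F/U Visit 5 or to the blood-draw windows follows from this point. If Day 43 is confirmed as an AE assessment, the cost is a schedule amendment and one brief AE contact per patient at an already scheduled visit, with no extra blood draw. The second item adds no visit.

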6.1.4 Short term follow up (q4 week visits x3 following Efficacy/Scan visit)

Unless subjects have radiographic progression, withdraw from study, or initiate new treatment, the following procedures must be completed every 4 weeks (+/- 7 days) after the initial efficacy/scan visit:

- Targeted Physical Examination with vital signs and weight
- Interim Medical History
- ECOG Performance Status
- CBC with differential and platelet count
- CMP (with direct bilirubin with known Gilbert's syndrome)
- PSA
- LDH

These q4-week lab/clinic visits may be performed with any licensed provider at any CLIA certified lab, provided that the results are available/provided to the Investigator within allowable windows. Visits associated with repeat CT and bone scan (q12 weeks until radiographic progression) should be performed at the WCM investigative site.

6.1.5 Long Term Follow Up

Following cancer progression, survival assessment and relevant medical history to be collected until death. Information may be collected from external providers. Information will be updated at least every 6 months following disease progression.

6.2 Treatment Administration

Treatment will be administered on an outpatient basis. Reported adverse events and potential risks are described in **Section 13**.

6.2.1 Agent Administration

Treatment will be administered only to eligible subjects under the supervision of the investigator or identified co-investigator(s). Treatment will be administered on an outpatient basis. Reported adverse events and potential risks are described in **Section 13**. Appropriate dose modifications/delays of the study drug are described in **Section 7**. No investigational or commercial agents or therapies other than those described below may be administered with the intent to treat the subject's malignancy.

